## III. APPROACH

We propose a two-center, randomized, double blind, placebo-controlled, parallel, three-episode, clinical trial of rizatriptan 10 mg oral tablets versus placebo for treating spontaneous vestibular attacks in patients with VM.

Our primary Specific Aim is to test hypotheses 1a-1d that rizatriptan will be:

- 1a. Superior to placebo in reducing the severity and duration of vestibular attacks as measured by:
  - (1) Proportion of treated attacks in which subjects experience a reduction in severity rating from Grade 3/2 to Grade 1/0 at one hour after taking study medication (see below for rating description). This is the main outcome measure; 1a(2)-1d(2) are secondary outcome measures.
  - (2) Proportion of treated attacks in which subjects achieve sustained relief (i.e., vestibular symptom severity rating of Grade 1/0) for 24 hours after taking study medication, without use of non-study therapies.
  - (3) Proportion of treated attacks in which subjects experience freedom from vestibular symptoms (i.e., severity rating of Grade 0) at one hour after taking study medication.
  - (4) Use of fewer non-study therapies after each attack treated with study medication.
- 1b. Superior to placebo in reducing severity of symptoms associated with vestibular attacks as measured by:
  - (1) Proportion of treated attacks in which subjects experience relief (reduction to Grade 1/0) from VM-associated symptoms (e.g., nausea, vomiting, motion sensitivity, gait disturbance, headache, photophobia, and phonophobia) at one hour after taking study medication.
  - (2) Proportion of treated attacks in which subjects achieve sustained relief from VM-associated symptoms for 24 hours after taking study medication without use of non-study therapies.
- 1c. Superior to placebo on treatment satisfaction and health-related quality of life as measured by:
  - (1) Scores on the Treatment Satisfaction Questionnaire for Medication (TSQM) at 48 hours after each attack treated with study medication
  - (2) Scores on the Short Form 12 (SF-12) at 48 hours after each attack treated with study medication
- 1d. Tolerated as well as placebo by patients with VM as measured by:
  - (1) No greater rate of treatment-emergent serious adverse events reported on the NCI Common Toxicity Criteria Scale 4.0^59 obtained 48 hours after each attack treated with study medication.

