**Table 2. Study Procedures and Rating Scales**

Procedures	Visit 1 Enrollment	Observation Phase	Visit 2 Randomization	Treatment Phase	Visit 3 End Point
Obtain informed consent	X				
Abstract medical record data	X				
Verify enrollment criteria	X				
Characterize baseline symptoms	X				
Instruct re Vestibular Symptom Diary	X		X		
Assess & stabilize comorbidity		1 st 3 months			
Review Vestibular Symptom Diary		Monthly	X	Monthly	X
Update health & medication list		Monthly	X	Monthly	X
Randomize for treatment			X		
Instruct re study treatment			X		
Dispense drug/placebo			X		
Treat 3 attacks				X	
Pregnancy Test			X		
Rating Scales					
Dizziness Handicap Inventory 	X		X		X
Anxiety Scale (GAD-7) 	X		X		X
Depression Scale (PHQ-9) 	X		X		X
Vestibular Symptom Diary		X		X	
Common Toxicity Criteria Scale 4.0 				X	
Treatment Satisfaction (TSQM) 				X	
Quality of Life Scale (SF-12) 	X		X	X	X
NEO-PI-3 Personality Inventory 	X				

**E. Outcome and Safety Measures (#1-4 mirror measures used in Phase III registration trials of rizatriptan)**

- 1. Vestibular Symptom Diary.** During Observation and Treatment Phases of the study, subjects will track the frequency of their headaches vestibular symptoms (unsteadiness/dizziness), and sensitivity to potential triggers of attacks (head/body motion, environmental stimuli, specific positions).
- 2. Common Toxicity Criteria Scale 4.0** (National Cancer Institute). A clinician-rated, comprehensive measure of toxicity from study medications in all body systems.
- 3. Treatment Satisfaction Questionnaire for Medication** (TSQM). A validated self-report measure of treatment satisfaction in four domains: effectiveness, side effects, convenience, and global satisfaction. Subjects will be asked whether they think they received rizatriptan or placebo after each dosing
- 4. Short Form 12** (SF-12). A 12-item self-report measure of health-related quality of life in six domains.
- 5. Dizziness Handicap Inventory** (DHI). A 25-item self-report of vertigo, dizziness, functional impairment, and emotional symptoms associated with vestibular symptoms.

6. **Generalized Anxiety Disorder Scale (GAD-7).** A 7-item self-report rating scale for anxiety, a common comorbidity of VM. The GAD-7 has cut-offs for clinically significant levels of anxiety symptoms.

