**3. Statistical Analysis and Modeling.** We will use SAS and R^70 statistical software, creating ad hoc algorithms and macro procedures to solve analytical questions for which no marketed algorithms exist.

1. As a first step to understanding the nature of our data, we will conduct univariate analysis of demographics, primary and secondary outcome measures, illness-related variables (e.g., frequency, severity, and duration of vertigo attacks), associated symptoms, comorbid conditions, and self-report rating scales. The marginal distribution of each measure will be calculated at each time point and across time. The time trends of outcome measures will be evaluated by graphical analyses. For example, parallel plots for each of the outcome measures will be created to examine the patterns of change over time.

2. We will test the four hypotheses of Specific Aim #1 using bivariate methods and multivariate modeling. First, we will analyze differences between rizatriptan and placebo on all outcome measures at each time point using chi-squares to cross-tabulate categorical variables, and t-tests, analyses of variance (ANOVAs), or marginal regressions to compare continuous variables.

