3. After testing bivariate differences, we will use repeated measures mixed effects models to compare outcome measures between rizatriptan and placebo over time, and examine the effects of covariates on treatment response. As an example, for the special case of binary outcome vertigo severity (Grade 3/2 versus Grade 1/0) and the more general case of ordinal outcome vertigo severity (Grade 3, 2, 1, 0), we will use SAS PROC GLIMMIX to model the logits of cumulative probabilities including vectors for study drug, illness related variables, associated symptoms, rating scales, random effects, and time. The estimates on the linear scale will represent log cumulative odds. The cumulative logits are formed as  $\log \{ \Pr(Y_i \leq j) / \Pr(Y_i > j) \} = X_i \alpha + Z_i \gamma_i + \varepsilon_i$  for  $i=1, \dots, n$ , where  $Y_i$  is the  $n_i \times 1$  vector of the outcome measure for the  $i^{\text{th}}$  patient,  $j=0,1,2,3$ ,  $n_i$  is the number of measurements for the  $i^{\text{th}}$  subject in the period,  $X_i$  is  $n_i \times p$  known predictors (indicator signifying rizatriptan and placebo, and time variable.) The fixed effects parameter vector of  $\alpha$  is  $p \times 1$ .  $Z_i$  is  $n_i \times k$  known predictors, which are associated with the random part of the model, including time-varying and time factors.  $\gamma_i$  is the  $k \times 1$  random effect parameter vector and  $\gamma_i \sim N(0, D)$ ,  $\varepsilon_i$  is  $n_i \times 1$  and  $\varepsilon_i \sim N(0, \sigma^2 I)$ , which is independent of  $\gamma_i$ . Let

$\Sigma_i(\theta) = Z_i D Z_i^T + \sigma^2 I$  with  $\theta$  being the parameter of covariance vector. Integrating out  $\gamma_i$  in the above random effect model, we can write  $Y_i \sim N(X_i \alpha, \Sigma_i(\theta))$ .

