Once they have experienced two qualifying vestibular attacks or at the end of the Observation Phase, subjects will return to their study center for a second visit. Investigators will collect interval history and subjects will complete the self-report measures listed in Table 2. This visit is expected to last 2 hours. Subjects who experience at least two vestibular attacks of moderate or greater severity during the Observation Phase and demonstrate acceptable adherence with data gathering and reporting procedures will be randomized to treat three subsequent vestibular attacks with either rizatriptan or placebo (ratio 2:1) in randomized and double-blind fashion. Subjects will rate treatment response and adverse effects. They will contact study personnel to review these data at 48 hours after each vestibular attack treated with study medications. The research coordinator will contact subjects on a monthly basis by phone to review progress, assess adherence, and gather data on any interval change that might affect treatment response or safety. The Treatment Phase may last as short as 6 days for subjects who have three vertigo attacks in quick succession after randomization to as long as 4 years for subjects who enroll at the start of the study and do not have 3 treatable attacks before the end of the study. Subjects will return to the study site for an End Point Visit (visit 3) as soon as possible after treating three attacks or sooner if they will be withdrawn from the study for any reason. The End Point Visit is expected to last 2 hours.

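### The plan never commits to adjusting 48-hour SF-12 for the Visit 2 score, and does not say which analysis step decides outcome 1c(2)

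*Combined protocol and SAP*

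**What the plan says.** Outcome 1c(2), listed at the start of section III (Approach), opens with "Scores on the Short Form 12 (SF-12" and is taken 48 hours after each treated attack, so a subject can contribute up to three values. In Table 2 the row beginning "Quality of Life Scale (SF-12" is marked at Visit 1, Visit 2 (randomization), the Treatment Phase and Visit 3. Section IV.B confirms the Visit 2 measurement: "Investigators will collect interval history and subjects will complete the self-report measures listed in Table 2". That visit comes before any study drug is taken.

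Section III.J.3 sets out the analysis in numbered steps:

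- Item 2 opens with "We will test the four hypotheses of Specific Aim #1 using bivariate methods and multivariate modeling". For continuous outcomes it then prescribes "t-tests, analyses of variance (ANOVAs), or marginal regressions to compare continuous variables". No covariate is named.
- Item 3 follows with repeated-measures mixed models to "compare outcome measures between rizatriptan and placebo over time, and examine the effects of covariates on treatment response". Its worked example is vertigo severity, in a model "including vectors for study drug, illness related variables, associated symptoms, rating scales, random effects, and time". The formula's fixed predictors are then described more narrowly: "indicator signifying rizatriptan and placebo, and time variable".
- Item 4 sends every outcome under hypotheses 1a to 1d through the same steps. It says that the principal result rests on 1a(1) plus tolerability. It does not say which step decides 1c(2).

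**The concern.** A pre-treatment measurement of the outcome's own scale is usually a strong predictor of the later score. Using it as a covariate narrows the interval and corrects for chance imbalance between the arms, which is worth having with about 40 placebo subjects planned. The trial already collects this measurement, so the benefit costs nothing.

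The plan leaves its use open. An unadjusted t-test, a mixed model with treatment and time only, and a mixed model that includes Visit 2 SF-12 would all comply with the text. They have different precision and can give different answers, and nothing says which one counts. Section III.J.1 gives the secondary outcomes no sample-size basis, so efficient analysis is the main way left to sharpen 1c(2), which item 4 says will inform the design of future trials.

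**Working it through.** **1. Does any text commit to the Visit 2 score?** Item 2 names no covariate. Item 3 has two descriptions that do not match: the prose for the vertigo example includes rating scales without saying which scale or which visit, while the formula lists only treatment and time. Item 4 extends the procedure to SF-12 without adding a covariate. By contrast, section IV.D.4 says that PHQ-9 is measured so that depression can be controlled for; no such purpose is stated for SF-12. The answer is no.

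**2. The plan's own figure.** The plan states no power, SD or correlation for SF-12. Its only sample-size statement concerns 1a(1): 120 subjects at 2:1, two-sided 0.05, 80% power, odds ratio 3.2. With placebo response 0.22, the active rate is p = 3.2 × (0.22/0.78) / [1 + 3.2 × (0.22/0.78)] = 0.474. The two-proportion formula with pooled variance and no continuity correction gives 79.0% power at 80 versus 40, and a required N of 123. That agrees with the stated 120, and SF-12 adjustment does not touch it.

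**3. Gain for SF-12 with one 48-hour value per subject.**

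Inputs: 80 versus 40 (120 subjects at 2:1, section III.J.1), two-sided 0.05, differences in SD units. The correlation rho between Visit 2 and 48-hour SF-12 is not in the documents; 0.3 to 0.7 is an assumed range. The 0.5 SD difference is illustrative.

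- Unadjusted SE = sqrt(1/40 + 1/80) = 0.194 SD.
- Detectable difference at 80% power = (1.960 + 0.842) × 0.194 = 0.543 SD.
- Power for 0.5 SD = Φ(0.5/0.194 − 1.960) = 73.3%.
- Adjusted variance = (1 − rho²) × unadjusted variance, so the SE is multiplied by sqrt(1 − rho²).
- Equivalent unadjusted N = 120 / (1 − rho²).

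| rho (assumed) | Variance ratio | Detectable difference | Power for 0.5 SD | Equivalent unadjusted N |
|---|---|---|---|---|
| none | 1.00 | 0.543 SD | 73.3% | 120 |
| 0.3 | 0.91 | 0.518 SD | 77.2% | 132 |
| 0.5 | 0.75 | 0.470 SD | 84.6% | 160 |
| 0.7 | 0.51 | 0.387 SD | 95.1% | 235 |

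**4. Up to three attacks per subject.** For the mean of three values with between-attack correlation ICC, the unadjusted variance is V0 = (1 + 2 × ICC)/3, and the adjusted variance is V0 − rho². At an assumed ICC of 0.5, V0 = 0.667. The variance ratio is then 0.577/0.667 = 0.87 at rho 0.3, 0.417/0.667 = 0.63 at rho 0.5, and 0.177/0.667 = 0.27 at rho 0.7. The table in point 3 therefore does not carry over directly to repeated attacks; the gain also depends on the ICC, which the documents do not give.

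**The case against.** The strongest reply is that the plan already provides for covariates. A reader might infer from item 2 that SF-12 is tested only by an unadjusted t-test or ANOVA and that the baseline is discarded. The documents do not support that. Item 2 also allows marginal regressions and is presented as the first stage; item 4 takes SF-12 on to the mixed model; and SF-12 sits under the Rating Scales heading of Table 2, so the generic term in item 3 could cover the Visit 2 score. A model of outcomes over time could also take Visit 2 SF-12 as a repeated measure. All of this stands. It shows that adjustment is permitted, not that it is specified.

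The size is also uncertain. Section IV.B allows the Treatment Phase to last up to 4 years, so Visit 2 may be far from the attack, and the outcome follows an acute episode. A rho near 0.3, with a 9% reduction, is plausible. This stands too, and is why the low end is shown.

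A reader might also take the physical well-being result in the summary at the end of the document, 4.55 (1.14, 7.97), derive SE = (7.97 − 1.14)/3.92 = 1.74, and shrink it by sqrt(1 − rho²). That is unsupported: the summary reports a regression estimate without its covariates, so it may already be adjusted, and the single-measurement factor does not apply to up to three attacks.

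Finally, randomization keeps the unadjusted comparison unbiased, and the trial's principal result does not depend on SF-12. Both are correct and limit the importance of the point.

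**Conclusion.** The point holds as a gap in pre-specification with a free gain in precision attached. The plan does not name Visit 2 SF-12 as a covariate for 48-hour SF-12 and does not say which step is decisive for 1c(2). At the planned 80 versus 40, the gain ranges from slight to large, depending on the correlation. That range rests on an assumed rho and one value per subject, and no single figure can be fixed from the documents. It is not a bias, does not affect the primary outcome or its sample size, and concerns a secondary outcome with no power claim. It is a low-priority improvement.

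**What to change.** In section III.J.3, state that 1c(2) is decided by the step 3 model: a linear mixed model for the 48-hour SF-12 component score, with treatment, the Visit 2 score of the same component and attack number as fixed effects and a random subject effect. The random effect also accounts for correlation among a subject's attacks. State that the step 2 tests of SF-12 are descriptive, and make the formula's list of fixed predictors agree with the prose.

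This costs a sentence or two in the plan and needs no new data. Because a results summary is already attached, it should also say whether the reported SF-12 estimates included the Visit 2 score. If they did not, the adjusted analysis can be reported alongside, labelled as not pre-specified.

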4. We will use this 3-step analysis procedure to test all outcome measures for hypotheses 1a-1d. However, the principal result of the study will be determined by the findings of bivariate analyses and multivariate modeling of the main outcome measure, 1.a.(1), plus favorable findings on tolerability measures, 1d(1)-1d(2). We will include all subjects who treat at least one vertigo attack with study drug (i.e., intent-to-treat analysis). A statistically significant result favoring rizatriptan over placebo on 1a(1) and absence of statistically significant differences on 1d(1)-1d(2) will support development of a Phase III clinical trial of rizatriptan for treating vestibular attacks in patients with VM. The design of future trials will also be informed by results of tests of secondary measures 1a(2)-1c(2). We did not hypothesize equal tolerability for rizatriptan and placebo, but rather an absence of significantly higher rates of serious adverse effects and drug-related treatment discontinuation, so our statistical analyses of measures 1d(1)-1d(2) will not include equivalence tests.

[figure not shown]

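### The model that helps decide the 1-hour primary outcome is not tied to the 1-hour rating, and its covariates are not limited to values known before dosing

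*Combined protocol and SAP*

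**What the plan says.** Section III (Approach) defines 1a(1) as the proportion of treated attacks with a "reduction in severity rating from Grade 3/2 to Grade 1/0 at one hour after taking study medication". Under section III.D.4, vestibular and associated symptoms are rated at dosing and then 0.5, 1, 2, 4, 24 and 48 hours later, and the TSQM and SF-12 are completed at 48 hours. Section III.G allows other symptomatic medication from 1 hour, and says the delay protects the primary outcome.

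Section III.J.3 sets out the analysis.

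- Item 2 compares arms at each time point by chi-square, so an unadjusted 1-hour test exists.
- Item 3 then uses repeated measures mixed models to "compare outcome measures between rizatriptan and placebo over time, and examine the effects of covariates on treatment response". An example for vertigo severity will "model the logits of cumulative probabilities including vectors for study drug, illness related variables, associated symptoms, rating scales, random effects, and time". The fixed-effects matrix is described as "known predictors (indicator signifying rizatriptan and placebo, and time variable". The random-effects matrix holds predictors "which are associated with the random part of the model, including time-varying and time factors".
- Item 4 applies the procedure to every outcome in 1a-1d and says "the principal result of the study will be determined by the findings of bivariate analyses and multivariate modeling of the main outcome measure", together with tolerability.
- Item 5 repeats the modeling as exploratory work, adding Treatment Phase data on 2a-2c.

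**The concern.** The primary question concerns one time point, but the written model is described as a comparison over time with a single drug term. Two things follow if it is applied literally.

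First, with seven ratings per attack available and no drug-by-time term, the drug coefficient is a weighted average over rating times. That average takes in ratings made after other medication is allowed, which section III.G was written to keep out of the primary outcome.

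Second, the covariates carry no timing. Item 1 counts attack severity and duration among the illness-related variables, while hypothesis 1a is "Superior to placebo in reducing the severity and duration of vestibular attacks as measured by" the listed endpoints. Post-dose associated symptoms are outcome 1b, and the TSQM and per-attack SF-12 are outcome 1c. Conditioning on any of these removes part of the effect being estimated.

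At stake is the Phase III decision, which item 4 ties to significance on 1a(1) without saying what happens if the chi-square and the model disagree.

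**Working it through.** **1. What the sample size assumes.** Section III.J.1 states 120 subjects at 2:1, two-sided 0.05, 80% power and a detectable odds ratio (OR) of 3.2. It does not state the placebo rate used; I assume 22%, from the earlier triptan trial that it cites.

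- Drug odds = 3.2 × 0.22/0.78 = 0.903, so the drug rate is 47.4%.
- With 80 and 40 subjects, the pooled SE is 0.0944 and the unpooled SE 0.0861.
- Power = Φ[(0.254 − 1.96 × 0.0944)/0.0861] = Φ(0.805) = 79.0%. Exactly 80% needs N = 123.

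The plan's figure therefore reproduces as one two-proportion comparison with one response per subject. It was not sized for a time-averaged coefficient.

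**2. Crude odds ratios from the Results section at the end of the document** (clustering ignored, Wald 95% intervals).

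| Outcome | Calculation | OR (95% CI) |
|---|---|---|
| Vertigo, 1 h | (73 × 39)/(80 × 53) | 0.67 (0.40-1.13) |
| Unsteadiness/dizziness, 1 h | (29 × 81)/(124 × 11) | 1.72 (0.81-3.64) |
| Unsteadiness/dizziness, 24 h | (120 × 36)/(29 × 52) | 2.86 (1.59-5.15) |

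**3. What a drug + time model does with the two unsteadiness/dizziness times.**

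- The log ORs are 0.544 (SE 0.382) and 1.052 (SE 0.300), with inverse-variance weights 6.86 and 11.13.
- Weighted mean = (6.86 × 0.544 + 11.13 × 1.052)/17.99 = 0.858, an OR of 2.36.
- The logistic fit with drug + time gives 2.38 (1.49-3.81), z = 3.61, naive p = 0.0003. With drug-by-time, the 1-hour OR returns to 1.72.
- Difference between times: z = (1.052 − 0.544)/√(0.382² + 0.300²) = 1.05. A changing effect is not shown.

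**4. Rough allowance for clustering.** The reported p-values (0.28, 0.24, 0.008), set against naive chi-square values (0.13, 0.15, 0.0003), imply variance inflation of 1.93, 1.49 and 1.82. This assumes that they are clustered versions of the same contrasts. With inflation of 1.5-1.9 and an assumed correlation of 0-0.5 between the two log ORs, the pooled p is 0.003-0.03. The reported 1-hour p is <0.24.

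**5. Consequence under each decision rule.** Simulation with 76 and 38 subjects (114 randomized, exact 2:1 assumed), 153 and 92 attacks, ratings at 1 h and 24 h, subject-clustered standard errors and assumed latent subject correlation of 0.1-0.5.

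- No 1-hour effect (12% in both arms), reported 24-hour rates: the pooled model is significant in 51-72% of trials and the 1-hour test in 2-3%. Both together are significant in 2-3%.
- 38% against 22% at 1 h, no 24-hour difference: requiring both gives 24-34% power, against 57-70% for the 1-hour test alone.
- Constant OR of 2.1: no bias (2.1 against 2.1).

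**6. Covariates, assumed example.** The covariate is 1-hour associated-symptom relief: 30% on placebo, drug OR 2.1, latent correlation with the outcome 0.3-0.7. Adjusting for it lowers the 1-hour OR from 2.1 to 1.9-1.6, and power from about 60% to 43-24%. If the drug does not change the covariate, nothing is lost.

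**The case against.** The strongest reply is that item 4 speaks of modeling 1a(1) itself, which is one binary result per attack. A model of that outcome has no rows at other times, and repetition would then mean repetition over up to three attacks. The severity model is offered only as an example, and the description of its fixed effects may be abbreviated. This is a fair reading and may be the more natural one. It stands as a limit on the point, but the plan does not state it, and the comparison over time in item 3 points the other way.

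The second reply is that the 1-hour chi-square is unaffected. If both analyses must agree, it blocks a false positive; step 5 confirms this, and that part stands. It does not prevent the loss of power, and item 4 does not say that both must agree.

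On covariates, item 5 adds Treatment Phase data on 2a-2c only in the exploratory repeat, which suggests earlier values in the first fit. Pre-dose versions of most listed variables exist. Associated symptoms, however, are not among 2a-2c, so item 5 does not settle their timing.

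The illustration is also narrow. It uses two of six post-dose times and a symptom other than the vertigo in the example. Vertigo at 1 hour runs the other way and has no reported 24-hour count.

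A reader might infer that the reported trial used a pooled model. The documents do not support that: the Results section gives separate 1-hour and 24-hour p-values.

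**Conclusion.** The point holds as an ambiguity worth closing before analysis. The only specification written for the model half of the primary decision does not target the 1-hour effect. Taken literally over all ratings, it targets a time-averaged effect that includes ratings after other medication is allowed. The two coincide only if the OR is constant over time, which the plan neither states nor justifies and the reported counts do not refute.

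The size depends on an unstated decision rule. If the chi-square and the model must both be significant, the main cost is power when an early effect fades: 24-34% against 57-70% in the assumed case. Frequent false positives would arise only if the model may override the 1-hour test, and item 4 does not say that it may. A reader could take the 51-72% figure as the plan's false-positive rate; the documents do not support this.

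Nor do they say that post-dose covariates will be used, only that nothing excludes them. The simulated figures rest on assumed correlations and time courses, and the pooled OR of 2.38 is an illustration, not an estimate of bias in the trial's result.

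**What to change.** In section III.J.3, state that the 1a(1) model is a logistic model of the 1-hour response for each treated attack, repeated over attacks and clustered by subject. Alternatively, include drug by categorical time and name the 1-hour contrast as the test.

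Restrict its covariates to values fixed before dosing, such as the attack's pre-dose grade, Observation Phase attack frequency and Visit 1 or 2 scales. Analyse post-dose associated symptoms, TSQM and per-attack SF-12 only as outcomes. Make the covariate list in the text agree with the fixed-effects matrix, and say whether the chi-square or the model prevails if they disagree.

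The cost is SAP wording and slightly more analysis work. No new data are needed, because pre-dose grades, Observation Phase diaries and the visit scales are already collected.

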## **J. Statistical Methods**

**1. Power Analysis.** The primary goal of this Phase II study is to demonstrate sufficient superiority of rizatriptan over placebo in the main outcome measure, 1a(1), to warrant a future Phase III trial. In the previous triptan study for VM (see Prior Controlled Study of Triptans for VM), the response rate for active drug was 3/8 (38%) versus 2/9 (22%) for placebo. If the small sample from that failed trial reflected a true response, then the odds ratio favoring the triptan for VM would be 2.1. To improve our estimate, we examined the results of two large registration trials that used a simple randomization design similar to the present proposal to test rizatriptan for conventional migraine. Those studies had response rates of 74% and 77% for rizatriptan versus 28% and 37% for placebo giving odds ratios of 7.4 and 5.7 favoring rizatriptan. The lower response rates in the VM trial most likely reflected the inadequate sample size, but could suggest that triptans are less effective for VM than conventional migraine. To account for this possibility, we took the limited results of Neuhauser, et al. as a worst-case scenario for our sample size calculation. Focusing on the main outcome measure, 1a(1), in this double-blind, randomized trial, with PASS simple randomization design and using a type I error of 0.05, type II error of 0.2 (equivalent to power of 80%), two-sided tests, then treating 120 subjects (with 2:1 ratio for treatment and placebo) will allow us to detect an odds ratio as small as 3.2. Thus, the plan to enroll 200 subjects in the Observation Phase and select 120 for the Treatment Phase will be sufficient, even if the response of VM to rizatriptan proves to be only half that of conventional migraine. Phase II trials typically gather data on secondary outcomes (e.g., 1a(2)-1d(2)) and other variables (2a-c) to inform the design of Phase III trials, but sample sizes need not be planned to demonstrate significant differences in these variables.

**2. Randomization.** A randomization scheme will be developed to assign the 120 patients expected to be included in the Treatment Phase to parallel treatment arms in a 2:1 ratio of active drug:placebo.

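### The mixed model printed for the binary and 0–3 vertigo grade is not a valid cumulative-logit model, and no estimation method is named; one reading of it would understate the subject-specific odds ratio

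*Combined protocol and SAP*

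**What the plan says.** Item 3, step 3 of III.J, Statistical Methods, offers the model as an example covering the "binary outcome vertigo severity (Grade 3/2 versus Grade 1/0") and "the more general case of ordinal outcome vertigo severity (Grade 3, 2, 1, 0"). For these, "we will use SAS PROC GLIMMIX" is the software statement; neither quadrature, Laplace nor pseudo-likelihood is mentioned. The log of Pr(Y ≤ j)/Pr(Y > j), for j = 0, 1, 2, 3, is set equal to a fixed part plus a random part plus a residual distributed N(0, σ²I). The random effects are then integrated out, and "in the above random effect model, we can write" Y as normal with mean Xα and covariance ZDZᵀ + σ²I. The same paragraph says: "The estimates on the linear scale will represent log cumulative odds".

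The binary split is the main outcome, 1a(1) in III. Approach. Step 4 makes multivariate modeling of 1a(1), alongside the bivariate tests, part of what decides the principal result, and applies the three-step procedure to every outcome under 1a–1d. Step 5 reuses the model for Specific Aim 2.

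**The concern.** The paragraph mixes two incompatible models: a logit model for a categorical grade and a linear normal model for a continuous score. An analyst cannot follow both. The logit statement gives an odds ratio; the normal marginal, taken literally, gives a difference in means or proportions.

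At stake is the estimate reported for the main outcome. The chi-square in step 2 carries no stated allowance for repeated attacks within a subject, so this model is the only described analysis of 1a(1) with a subject random effect. The trial exists to guide a Phase III design. Two analysts working from this paragraph could report materially different odds ratios from the same data.

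**Working it through.** **1. The plan's own figure.** No figure is given for the mixed model. The power section, "using a type I error of 0.05, type II error of 0.2 (equivalent to power of 80%), two-sided tests", states: "then treating 120 subjects (with 2:1 ratio for treatment and placebo) will allow us to detect an odds ratio as small as 3.2". The same section records that in the earlier VM trial "the response rate for active drug was 3/8 (38%) versus 2/9 (22%) for placebo".

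Take placebo p0 = 0.22. The odds are 0.22/0.78 × 3.2 = 0.903, so p1 = 0.903/1.903 = 0.474, and the 2:1 pooled rate is p̄ = (40 × 0.22 + 80 × 0.474)/120 = 0.390. Then

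n0 = [1.96 √(1.5 p̄(1−p̄)) + 0.842 √(p0(1−p0) + p1(1−p1)/2)]² / (p1−p0)² ≈ 41,

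which gives 123 in total against the stated 120, with power 0.790 at 40:80. The figure reproduces as an ordinary two-proportion calculation, does not use the mixed model, and is unaffected by this point.

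**2. The printed equations.**
- *Residual.* For a binary or ordinal outcome, Bernoulli or multinomial sampling around the modeled probability supplies the row-level variation. An added N(0, σ²) term on the logit changes the meaning of the coefficient: a coefficient of ln 3.2 then corresponds to an odds ratio of 3.02, 2.88, 2.66 or 2.38 without that term, for σ² of 0.25, 0.5, 1 or 2.
- *Cut-points.* The right-hand side does not depend on j. Hence Pr(Y ≤ 0) = Pr(Y ≤ 1) = Pr(Y ≤ 2), and grades 1 and 2 would have probability zero.
- *j = 3.* Pr(Y ≤ 3) = 1 and Pr(Y > 3) = 0, so the logit is infinite.
- *Normal marginal.* A grade taking two or four values cannot be normal. Under it the treatment coefficient is a difference in means. With the rates above, the binary version would estimate 0.474 − 0.220 = 0.254, whereas the log odds ratio is ln 3.2 = 1.163.

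**3. If the normal step is read as a linearized (pseudo-likelihood) fit.** This is an assumption, since no method is stated.

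Inputs: a random-intercept logit model, true subject-specific odds ratio 3.2, marginal placebo response 22%, 2:1 allocation. Rows per subject: at most three for the 1-hour outcome. The appended results summary gives 245 usable attacks in 114 randomized subjects, 245/114 = 2.15 each. The documents give no between-subject variance, so a range is shown. Large-sample limits:

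| Subject variance (SD) | Linearized OR, 3 attacks | Log-OR too low by | Linearized OR, 2 attacks | Four-grade outcome, 3 attacks | True marginal OR |
|---|---|---|---|---|---|
| 0.25 (0.5) | 3.03 | 5% | 3.02 | – | 3.02 |
| 0.5 (0.71) | 2.90 | 8% | 2.89 | 3.07 | 2.88 |
| 1 (1) | 2.72 | 14% | 2.68 | 2.99 | 2.66 |
| 2 (1.41) | 2.49 | 22% | 2.43 | 2.87 | 2.38 |
| 4 (2) | 2.23 | 31% | 2.14 | 2.71 | 2.08 |

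The shortfall is 1 − ln(OR)/ln 3.2; at variance 1, 1 − 1.001/1.163 = 0.14. At zero variance there is no bias. Quadrature maximum likelihood recovers 3.20 (checked at variances 1 and 4). The marginal column averages the response over the random intercept. At variance 1 the rates are 22% and 42.9%, giving (0.429/0.571)/(0.22/0.78) = 2.66; at variance 4 they are 22% and 36.93%, giving 2.08.

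**4. At the trial's size** (80/40 subjects, three attacks, 400 runs). Rejection rates are linearized v quadrature:

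| | Variance 1 | Variance 2 |
|---|---|---|
| Median OR, true 3.2 | 2.77 v 3.25 | 2.62 v 3.33 |
| Rejection, OR 3.2 | 0.953 v 0.953 | 0.840 v 0.843 |
| Rejection, OR 2.1 | 0.542 v 0.560 | 0.417 v 0.425 |
| Rejection, null | 0.055 v 0.052 | 0.037 v 0.035 |

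Monte Carlo error is about 1 to 2.5 percentage points. A separate simulation of the same design gave linearized medians of about 3.1, 2.8, 2.4 and 2.2 at SD 0.5, 1, 1.5 and 2, against 3.1–3.4 by quadrature. The fitted subject SD was shrunk as well.

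**5. If every post-dose rating is modeled.** Six post-dose times over three attacks give up to 18 rows per subject. With one shared intercept the linearized limit is 2.96 at variance 1 and 2.86 at variance 2.

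**The case against.** The strongest reply accepts that the equation is malformed and denies that any bias follows. The text names mixed-model software, cumulative logits and log cumulative odds, so a competent analyst would probably fit a sensible model. Linearized pseudo-likelihood treats a working variable as normal with mean-dependent variance; the protocol instead prints Y itself as normal with σ²I, so identifying the two is an inference. This stands: the understatement is conditional on a method the plan does not state.

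Second, the shortfall exists only against the subject-specific odds ratio. At variance 1 the linearized 2.72 lies close to the marginal 2.66, and the plan never says which it wants. This also stands, and is itself a reason to state the target.

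Third, the decision rule in step 4 turns on statistical significance, which hardly moves. A reader might infer from the defective equation that the primary test is invalid or that power is lost; the simulations do not support that.

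Fourth, n_i counts measurements over time, so three rows per subject is not what the paragraph literally describes. It is right for 1a(1), which is defined at one hour; with all times modeled the bias is smaller.

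Finally, a normal mixed model suits the TSQM and SF-12 scores, to which step 4 also applies the procedure. That calls for separating the two models. It does not rescue the logit equation.

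**Conclusion.** The concern holds in this form. As printed, the model for the Grade 3/2 v 1/0 and Grade 0–3 outcomes is invalid on four counts, none of which needs an assumption, and the estimation method is missing.

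The numerical consequence is conditional. If the normal step becomes a linearized fit to the 1-hour outcome, a true subject-specific odds ratio of 3.2 is estimated at about 3.0–3.1 at SD 0.5, 2.7–2.8 at SD 1 and 2.2 at SD 2. The log odds ratio is 5% to 31% low over variances 0.25 to 4. For the four-grade outcome it is 3% to 14% low over variances 0.5 to 4. These sizes rest on assumed between-subject variances, a 22% placebo response in the large-sample limits, and a single random intercept.

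A reader might go further and say that the trial's odds ratio will be understated by a fixed fraction, such as a fifth or a quarter. The documents do not support this: they give neither the fitting method nor the between-subject variance, and do not say which odds ratio is to be reported. What is exposed is the effect estimate carried into Phase III planning; type I error and power are essentially unchanged.

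**What to change.** Replace the equation in step 3 for the categorical outcomes with

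logit Pr(Y ≤ k | γ_i) = θ_k + xα + zγ_i, for k = 0, 1, 2,

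with no residual term and no normal marginal. For the binary primary, use a single intercept and one row per attack at one hour, and say which random effects are kept. Name the method: adaptive Gauss-Hermite quadrature, or Laplace if there are several random effects. State whether the reported odds ratio is subject-specific or marginal and, if marginal, how it is obtained. Print the normal mixed model separately and keep it for continuous outcomes such as TSQM and SF-12. No extra covariates are needed to cure this defect.

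The cost is a paragraph of SAP text and one fitting option, with slightly longer computation and possible convergence checks. Sample size, data collection and the significance rule do not change.
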